3. DEMOGRAPHICS AND BASELINE ASSESSMENTS

The following are specific demographic / baseline assessments of interest for analyses. Primary analyses will adjust for these covariates as we anticipate they will influence outcome. We plan to report both model-adjusted and simple unadjusted intervention effect estimates. In the cases of adjusted models, we will include the following variables as fixed effects, regardless of significance:

- 1) Sex [sex].
- 2) Age [age].
- 3) Race/ethnicity [ethnic]. We plan to categorize participants into White (ethnic = 1), Hispanic (ethnic = 3, 4, 5, 6), African American (ethnic = 2), or other categories. In the event of low cell counts in any one category, we may consider collapsing categories, foregoing adjustment for race (if collapsing cannot be justified scientifically), or failing to adjust for race altogether. We may also consider another potential covariate that is heavily related to race and ethnicity or conduct sensitivity analyses under different parameterizations / assumptions.
- 4) Literacy score according to the Newest Vital Sign (NVS, sum of [vs_totcal, vs_carb, vs_fat, vs_daily, vs_safe, vs_peanut]) as defined per scoring manual. The score ranges from 0-6, with 0-1 indicating limited literacy, 2-3 indicating likely limited literacy, and 4-6 indicating adequate literacy.
- 5) Indicator of monotherapy at baseline [inc04 = 3].

Additional demographics in general include:

- 1) Country of birth [birth].
- 2) Insurance status [insurance].
- 3) Education [edu].
- 4) Employment status [emplst].
- 5) Income [income_usd].
- 6) Marital status [marst].
- 7) Number of people in household [pple].

Note that some additional exploratory analyses may examine these additional demographic variables as covariates and/or effect modifiers as well. We will label any exploratory analyses involving additional potential covariates as post hoc in any dissemination materials.

4. DATA STORAGE

Data will be collected and managed using Research Electronic Data Capture (REDCap) housed at Northwestern University's Clinical and Translational Sciences Institute (CTSA), NUCATS [1].

REDCap is a secure, web-based application designed for research studies that provides an intuitive interface for validated data entry, audit trails for tracking data manipulation and export procedures,

and automated export procedures for seamless data downloads to common statistical packages, and procedures for importing data from external sources. Refer to the study Data Management Plan (DMP) for details.

5. RANDOMIZATION METHODS

We plan for equal allocation (1:1) across study arms; the study statistician (Co-PI: [name]) generated a randomization list using random block assignments (i.e., randomly varying block sizes). The details of the block sizes and number of blocks will remain confidential until study completion. The study statistician uploaded a “Development” randomization list and a separate “Production” randomization list into REDCap. Each participant will be assigned a randomly-generated kit number that will correspond to either an active comparator (candesartan) or investigational product (LDQT) drug kit. The randomization lists are housed on Northwestern University’s “FSMResFiles” with restricted access such that only unblinded individuals can access. Neither the study coordinator / study nurse / individual assigning the study kit numbers nor the participants will have ability to determine which kit numbers correspond to each arm as they were generated via a random uniform distribution with the seed number, block sizes, and subsequently sorted randomization lists restricted to this set of folders on Northwestern University’s servers. Randomization does not involve any stratification factors; however, with the addition of a second study site, the randomization is de facto stratified by site (i.e., each site has its own randomization sequence).

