## 11. RECRUITMENT METHODS

Participants will be recruited from two of the community clinics within Access Community Health Network using its Epic-based health information technology system. This system allows for rapid electronic identification of eligible participants based on routinely collected clinical data as well as direct communication with their clinicians to seek their permission to contact potential participants. This methodology has been used in numerous studies between Northwestern investigators and ACCESS for successful recruitment. Participants may be contacted for screening either by phone or through electronic messaging, through MyChart. After initial contact by phone or electronic messaging, participants may also be contacted via text for appointment scheduling and reminders and retention.

In the event of lagging recruitment or lack of diversity in study population to reach our targets, we plan to open up recruitment and enrollment efforts to additional Access Community Health Network site(s). If this occurs, then we will submit a protocol amendment and seek IRB approval prior to initiating study procedures at any additional sites.

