## 16.2. Statistical Analysis

The primary study analysis time point for all relevant outcomes is 12 weeks post randomization. The original analysis plan called for ANCOVA, controlling for baseline value of each relevant outcome in addition to the following baseline covariates: sex, age at baseline, race/ethnicity, health literacy level (indicator of limited literacy as defined by the Newest Vital Sign instrument), and an indicator of monotherapy at baseline (vs. untreated; this variable will serve as a stratification factor for randomization). These variables are deemed clinically relevant and important covariates; thus, all analyses will plan for adjustment for these covariates of interest (regardless of statistical significance in the current dataset) in predicting outcome in the present study. However, to better align with the analytic strategies of the QUARTET Australia study, and to make most efficient use of all follow-up data (both six-week and 12-week data), primary analyses will involve a linear mixed model with fixed study arm and baseline outcome value effects and a random participant effect to account for within-participant correlation. We plan to conduct both unadjusted (for potential covariates mentioned above) and adjusted analyses. The updated details of these analyses are reserved for the statistical analysis plan. The basic analytic model will be as follows for each outcome ( $Y$ ) for participant  $i$  ( $i=1\dots N$ ) at visit  $j$  ( $j=1,2$ ; corresponding to Week 6 and Week 12):

$$Y_{ij} = \beta_0 + \beta_1 I(LDQT) + B_2(Y_{0i}) + B_3 visit + B_4(visit \times study\ arm) + b_i + e_{ij}$$

Under the assumption that error terms  $e_{ij} \sim N(0, \sigma^2)$  is the random error term,  $b_i \sim N(0, \sigma_b^2)$  is the participant-level random effect. If visit-by-study arm ( $B_4$ ) is insignificant at the 5% level, we will remove that term from the model, and subsequently, we will further examine for an overall main effect for visit ( $B_3$ ). If insignificant, we will also remove that effect from the model and evaluate intervention effect via the primary hypothesis test of interest:

$$H_0: \beta_1 = 0 \text{ vs. } H_1: \beta_1 \neq 0$$

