6. STATISTICAL METHODS

Descriptive statistics will summarize participant demographics and baseline clinical outcomes overall and across arms: proportion (percentages) for categorical variables; mean (\pm standard deviation) for continuous variables; and median (interquartile range) for skewed or count variables. Analyses in general will employ normal theory methods and residual diagnostics will evaluate validity of assumptions; where appropriate (i.e., in the event of low cell counts for categorical data or questions of normality), transformation of variables, nonparametric methods, or exact tests may be employed. All primary efficacy and safety analyses will be pre-specified as outlined in this SAP, and deviations from planned analyses or post hoc analyses will be labeled as such in any reports or dissemination materials.

Analyses will assume a two-sided 5% type I error rate unless otherwise specified; there will be some exploratory analyses that will involve a relaxed type I error rate (10%). There will be no corrections made for multiple hypothesis tests, as this is a phase II study evaluating preliminary efficacy.

Planned Primary, Secondary, Safety Analyses

The primary study analysis time point for all relevant outcomes is 12 weeks post randomization. The original analysis plan called for an analysis of covariance (ANCOVA), controlling for baseline value of each relevant outcome in addition to the following baseline covariates: sex, age at baseline, race/ethnicity, health literacy level (indicator of limited literacy as defined by the Newest Vital Sign instrument), and an indicator of monotherapy at baseline (vs. untreated). We deem these variables clinically relevant, important covariates; thus, all analyses will plan for adjustment for these covariates of interest (regardless of statistical significance in the current dataset) in evaluating efficacy of intervention in the present study. However, to better align with the analytic strategies of the QUARTET Australia study, and to make most efficient use of all follow-up data (both six-week and 12-week data), primary analyses will involve a linear mixed model with fixed study arm and baseline outcome value effects and a random participant effect to account for within-participant correlation. We Statistical Analysis Plan: February 9, 2022

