plan to conduct both unadjusted (for potential covariates mentioned above) and adjusted analyses. The updated details of these analyses are reserved for the statistical analysis plan. The basic analytic model will be as follows for each outcome (Y) for participant i ($i=1\dots N$) at visit j ($j=1, 2$; corresponding to Week 6 and Week 12):

$$Y_{ij} = \beta_0 + \beta_1 I(LDQT) + B_2(Y_{0i}) + B_3 visit + B_4(visit \times study\ arm) + b_i + e_{ij}$$

Under the assumption that error terms $e_{ij} \sim N(0, \sigma^2)$ is the random error term, $b_i \sim N(0, \sigma_b^2)$ is the participant-level random effect. If visit-by-study arm (B_4) is insignificant at the 5% level, we will remove that term from the model, and subsequently, we will further examine for an overall main effect for visit (B_3). If insignificant, we will also remove that effect from the model and evaluate intervention effect via the primary hypothesis test of interest:

$$H_0: \beta_1 = 0 \text{ vs. } H_1: \beta_1 \neq 0$$

for each outcome. However, if the visit-by-study arm interaction term or the visit term alone is significant, we will plan to evaluate the 12-week contrast via model-estimated least squared means as our primary analyses. All between-arm differences at both six- and 12-week time points will be reported as model-based estimates, corresponding 95% confidence limits, and p-value of the corresponding hypothesis test.

Secondary analyses (i.e., those for the secondary and exploratory outcomes of interest) will utilize data from all time points via (generalized) linear mixed modeling (GLMM) methods with the following specifications: identity, logit, or log link for continuous, binary, or count outcomes, respectively; fixed arm, visit, visit-by-arm interaction, and aforementioned covariates; and random participant effect. For secondary analyses, the model adjusted Wald type III tests for fixed effects will first evaluate significance of a visit-by-arm interaction at the 5% level of significance. If insignificant at the 5% level, then this interaction term will be removed and the model Wald type III test for fixed arm effect will evaluate the overall intervention effect in this longitudinal model at the 5% level.

The table below summarizes the general modeling strategy for each outcome. In each case, we plan to conduct both adjusted and unadjusted analyses. Adjusted analyses will include the aforementioned covariates.

Table: Modeling Strategy by Outcome

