Outcome	Variable Type	Model Link Assumption	Note on Covariates
Primary, secondary / exploratory blood pressure measurements at individual study time points	Continuous (assume normality)	Identity	Same as in primary outcome analyses
Dipping at 12 weeks	Binary / categorical	Logit	Indicator of dipping status at baseline in addition to other covariates as in primary analyses
Hypertension control at individual study time points	Binary / categorical	Logit	Same as in primary outcome analyses, including baseline SBP
Requirement for amlodipine add-on therapy	Binary / categorical	Logit	Same as in primary outcome analyses, including baseline SBP
Adverse event-free hypertension control at each study time point	Binary / categorical	Logit	Same as in primary outcome analyses, including baseline SBP
Medication adherence (at least 80%)	Binary / categorical	Logit	Same as in primary outcome analyses, including baseline SBP
Change in PROMIS Global Health	Continuous (assume normality)	Identity	Same as in primary outcome analyses
Indicator for any SAE	Binary / categorical	Logit	Same as in primary outcome analyses, including baseline SBP
Indicator for any relevant side effect	Binary / categorical	Logit	Same as in primary outcome analyses, including baseline SBP
Rate of relevant side effects	Count (Poisson assumption)	Log	Same as in primary outcome analyses, including baseline SBP
Continuous laboratory measurements (potassium, sodium, urea, creatinine)	Continuous (assume normality)	Identity	Same as in primary outcome analyses

Subgroup Analyses and Heterogeneity of Intervention Effects

An exploratory objective of this study is to assess heterogeneity of treatment effect by the following potential hypothesized moderators: age, sex, and race/ethnicity. To address this, we will analyze primary and secondary blood pressure (12-week SBP, DBP) outcomes via the aforementioned

LMMs; we will add an arm-by-<potential moderator> effect in the original model specified above for each potential moderator of interest. Moderation effects will be explored via model-adjusted type III Wald test for fixed effects at the relaxed 10% level of significance. If significant, then we will examine the intervention effect within each subgroup via a series LMMs: male/female, age category, racial/ethnic category.

Agreement between Outcomes

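### Each site has its own randomisation list but site is in no planned model, and the protocol and SAP disagree on whether baseline monotherapy was a stratification factor

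*SAP*

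**What the plan says.** **Randomisation.** SAP section 5 states: "Randomization does not involve any stratification factors". The same sentence then adds that, with a second site, "the randomization is de facto stratified by site", because each site works from its own sequence. Protocol section 11 gives the number of sites: "Participants will be recruited from two of the community clinics within Access Community Health Network". It allows more to be added by amendment.

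**Models.** In SAP section 6, "primary analyses will involve a linear mixed model with fixed study arm and baseline outcome value effects and a random participant effect". The formula there, repeated in Protocol 16.2, also has visit and visit-by-arm terms. SAP section 3 says of the adjusted versions that "we will include the following variables as fixed effects, regardless of significance"; the list is sex, age, race/ethnicity, literacy score and baseline monotherapy. Secondary models use "fixed arm, visit, visit-by-arm interaction, and aforementioned covariates; and random participant effect". The outcome table in SAP section 6 points back to that set, for example "Same as in primary outcome analyses, including baseline SBP". The moderators are age, sex and race/ethnicity. Site is in none of these. Its only planned use is in the central monitoring summaries of Protocol section 16.

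**Monotherapy.** Protocol 16.2 says of the baseline monotherapy indicator that "this variable will serve as a stratification factor for randomization". SAP section 6 gives the same covariate list without that remark.

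**The concern.** When allocation is balanced within sites, the arm contrast is protected from site differences by design. An analysis that ignores site leaves the between-site variation in the residual. The reported standard error is then larger than the true one, so the test rejects less often than its nominal level and power falls. The error is in the conservative direction.

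The target has been cut from 365 to 87 randomised, with 77 expected in the analysis, so precision is scarce and a term that matches the randomisation is close to free. The SAP recognises the site stratification but gives no reason for leaving site out of the models.

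The second issue is one of record. The two statements on monotherapy cannot both be true, so a reader cannot tell whether balance on prior treatment was built in by design or left to chance.

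**Working it through.** **Inputs from the documents**
- N analysed = 77: 87 randomised with 12% dropout, 87 × 0.88 = 76.6 (SAP section 8).
- Treatment effect 6.9 mmHg, 95% CI 4.9 to 8.9, 591 patients (Protocol 2.3, Australian trial).
- Two-sided 5% level; planning SD 15 mmHg (SAP section 8).

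**Assumptions, not in the documents**
- Residual site difference d and site share p.
- Residual SD back-calculated from the Australian interval. The half-width is 2.0, so SE = 2.0/1.96 = 1.02 and SD = 1.02 × √591 / 2 = 12.4 mmHg.

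**Formula.** With balance within site, the true SE of the arm difference is 2·SD/√N whether or not site is modelled. Without site, the estimated SE is inflated by √(1 + p(1−p)d²/SD²). Type I error and power follow from the central and noncentral t distributions with 74 df (73 with site).

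**Main case: week 12 only, equal sites (p = 0.5)**
- True SE = 2 × 12.4/√77 = 2.83. With site in the model, power at 6.9 mmHg is 67.3%.
- d = 5: factor √(1 + 0.25 × 25/153.8) = 1.020, reported SE 2.88.
- d = 8: factor √(1 + 0.25 × 64/153.8) = 1.051, reported SE 2.97.

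| Case, site omitted | Type I error, d = 5 / 8 | Power loss in points, d = 5 / 8 |
|---|---|---|
| Week 12, 50:50, SD 12.4 | 4.6% / 4.0% | 1.4 / 3.7 |
| Week 12, 90:10, SD 12.4 | 4.8% / 4.6% | 0.5 / 1.3 |
| Both visits, 50:50, within-participant correlation 0.5 (assumed) | 4.4% / 3.7% | 1.5 / 4.0 |
| Week 12, 50:50, SD 15 | 4.7% / 4.3% | 1.1 / 2.7 |

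For two visits, with complete data and no interaction, SD becomes 12.4 × √((1 + 0.5)/2) = 10.7.

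At d = 3 and SD 12.4, week 12 only, the loss is 0.5 points at 50:50, 0.3 at 80:20 and 0.2 at 90:10. At d = 0 nothing is lost.

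**Simulation checks**
- 40,000 trials per scenario, permuted blocks of 4 or 6 within site (assumed), baseline SBP in the model, equal sites. Without/with site, type I error is 5.1/5.2% at d = 0, 4.7/5.0% at d = 5 and 3.9/5.0% at d = 8. Power is 65.0/66.4% at d = 5 and 63.1/66.9% at d = 8. At d = 0 the mean SE is 2.836 with site and 2.835 without, so including site costs nothing measurable.
- A separate simulation with 87 randomised, 12% random dropout, SD 15, baseline correlation 0.5 and equal sites. Power without/with site is 62.2/62.5% at d = 3, 61.3/62.8% at d = 5 and 57.2/62.3% at d = 10. Type I error without site is 4.9%, 4.5% and 3.7%.

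These power figures only compare models with and without site. They do not test the stated conditional power of over 90%, whose interim inputs are not given.

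**Monotherapy.** No arithmetic applies. Protocol 16.2 names it as a stratification factor. SAP section 5 denies any, and the list of updates in SAP section 9 records no change on this point.

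**The case against.** The strongest reply is that this is a matter of preference. The test errs on the safe side, so no positive finding is threatened, and power suffers only if the sites differ. Nothing in the documents suggests that they do: both clinics belong to one network, study drug is handled centrally and procedures are common. A residual gap of 5 to 8 mmHg is about the size of the treatment effect itself, and at 3 mmHg the loss is half a point or less. The second site was added later, so an equal split may be far from the truth. The adjusted models may already absorb part of any case-mix difference through race/ethnicity and literacy. The SD of 12.4 may come from a repeated-measures analysis, in which case shrinking it again for two visits overstates those losses somewhat.

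All of this bears on size, and it stands: the likely loss is small and could be nil. It does not supply a reason for leaving out a term that the randomisation already contains and that costs one degree of freedom.

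On monotherapy, the protocol remark is in the future tense, inside a sentence about the superseded ANCOVA. SAP section 5 reports in the past tense how the lists were generated, which makes it the more direct account. That also stands, and the protocol remark may well be a leftover. But it is current text about randomisation rather than about the ANCOVA model, and nothing withdraws it.

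**Conclusion.** The concern holds. The randomisation is stratified by site and no planned model contains site. The consequence is a slightly conservative test and some lost power, with no bias and no alpha inflation. Under the assumed inputs the loss runs from zero with no site difference, through about 0.5 to 1.5 points at 5 mmHg, to about 1.3 to 4.0 points at 8 mmHg, with equal sites the worst case. The site difference, site split, residual SD and within-participant correlation are all assumptions, and the figures adjust for baseline SBP only, not for the other planned covariates. The change is worth making because it is nearly free, not because the plan is unsafe without it.

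The monotherapy contradiction is real but is a matter of wording. The indicator is already a fixed covariate in the adjusted models.

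**What to change.** Before database lock:

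1. Add site as a fixed effect to the primary linear mixed model, in both its unadjusted and adjusted versions, and to the other continuous-outcome models. Say in the SAP that the unadjusted estimate then conditions on site as well as baseline. If site is left out, give the reason.
2. Add site to the binary and count models only where event numbers allow. At the pooled SAE rate in Protocol 9.1, (7 + 3)/591, about 10/591 × 77 = 1.3 participants with an SAE are expected, so that model cannot carry more terms.
3. Check the randomisation lists actually used and state the same stratification factors in Protocol 16.2 and SAP section 5. Keep monotherapy in the adjusted models as planned.

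The cost is one degree of freedom for two sites, one more for each site added by amendment, and a short wording correction. No new data are needed, because site is known from the separate sequences. Timing matters: SAP section 6 requires departures from the planned analyses to be labelled, so a site term added after lock would be reported as a deviation.

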6. STATISTICAL METHODS

Descriptive statistics will summarize participant demographics and baseline clinical outcomes overall and across arms: proportion (percentages) for categorical variables; mean (\pm standard deviation) for continuous variables; and median (interquartile range) for skewed or count variables. Analyses in general will employ normal theory methods and residual diagnostics will evaluate validity of assumptions; where appropriate (i.e., in the event of low cell counts for categorical data or questions of normality), transformation of variables, nonparametric methods, or exact tests may be employed. All primary efficacy and safety analyses will be pre-specified as outlined in this SAP, and deviations from planned analyses or post hoc analyses will be labeled as such in any reports or dissemination materials.

Analyses will assume a two-sided 5% type I error rate unless otherwise specified; there will be some exploratory analyses that will involve a relaxed type I error rate (10%). There will be no corrections made for multiple hypothesis tests, as this is a phase II study evaluating preliminary efficacy.

Planned Primary, Secondary, Safety Analyses

The primary study analysis time point for all relevant outcomes is 12 weeks post randomization. The original analysis plan called for an analysis of covariance (ANCOVA), controlling for baseline value of each relevant outcome in addition to the following baseline covariates: sex, age at baseline, race/ethnicity, health literacy level (indicator of limited literacy as defined by the Newest Vital Sign instrument), and an indicator of monotherapy at baseline (vs. untreated). We deem these variables clinically relevant, important covariates; thus, all analyses will plan for adjustment for these covariates of interest (regardless of statistical significance in the current dataset) in evaluating efficacy of intervention in the present study. However, to better align with the analytic strategies of the QUARTET Australia study, and to make most efficient use of all follow-up data (both six-week and 12-week data), primary analyses will involve a linear mixed model with fixed study arm and baseline outcome value effects and a random participant effect to account for within-participant correlation. We Statistical Analysis Plan: February 9, 2022

plan to conduct both unadjusted (for potential covariates mentioned above) and adjusted analyses. The updated details of these analyses are reserved for the statistical analysis plan. The basic analytic model will be as follows for each outcome (Y) for participant i ($i=1\dots N$) at visit j ($j=1, 2$; corresponding to Week 6 and Week 12):

$$Y_{ij} = \beta_0 + \beta_1 I(LDQT) + B_2(Y_{0i}) + B_3 visit + B_4(visit \times study\ arm) + b_i + e_{ij}$$

Under the assumption that error terms $e_{ij} \sim N(0, \sigma^2)$ is the random error term, $b_i \sim N(0, \sigma_b^2)$ is the participant-level random effect. If visit-by-study arm (B_4) is insignificant at the 5% level, we will remove that term from the model, and subsequently, we will further examine for an overall main effect for visit (B_3). If insignificant, we will also remove that effect from the model and evaluate intervention effect via the primary hypothesis test of interest:

$$H_0: \beta_1 = 0 \text{ vs. } H_1: \beta_1 \neq 0$$

for each outcome. However, if the visit-by-study arm interaction term or the visit term alone is significant, we will plan to evaluate the 12-week contrast via model-estimated least squared means as our primary analyses. All between-arm differences at both six- and 12-week time points will be reported as model-based estimates, corresponding 95% confidence limits, and p-value of the corresponding hypothesis test.

Secondary analyses (i.e., those for the secondary and exploratory outcomes of interest) will utilize data from all time points via (generalized) linear mixed modeling (GLMM) methods with the following specifications: identity, logit, or log link for continuous, binary, or count outcomes, respectively; fixed arm, visit, visit-by-arm interaction, and aforementioned covariates; and random participant effect. For secondary analyses, the model adjusted Wald type III tests for fixed effects will first evaluate significance of a visit-by-arm interaction at the 5% level of significance. If insignificant at the 5% level, then this interaction term will be removed and the model Wald type III test for fixed arm effect will evaluate the overall intervention effect in this longitudinal model at the 5% level.

The table below summarizes the general modeling strategy for each outcome. In each case, we plan to conduct both adjusted and unadjusted analyses. Adjusted analyses will include the aforementioned covariates.

Table: Modeling Strategy by Outcome

Outcome	Variable Type	Model Link Assumption	Note on Covariates
Primary, secondary / exploratory blood pressure measurements at individual study time points	Continuous (assume normality)	Identity	Same as in primary outcome analyses
Dipping at 12 weeks	Binary / categorical	Logit	Indicator of dipping status at baseline in addition to other covariates as in primary analyses
Hypertension control at individual study time points	Binary / categorical	Logit	Same as in primary outcome analyses, including baseline SBP
Requirement for amlodipine add-on therapy	Binary / categorical	Logit	Same as in primary outcome analyses, including baseline SBP
Adverse event-free hypertension control at each study time point	Binary / categorical	Logit	Same as in primary outcome analyses, including baseline SBP
Medication adherence (at least 80%)	Binary / categorical	Logit	Same as in primary outcome analyses, including baseline SBP
Change in PROMIS Global Health	Continuous (assume normality)	Identity	Same as in primary outcome analyses
Indicator for any SAE	Binary / categorical	Logit	Same as in primary outcome analyses, including baseline SBP
Indicator for any relevant side effect	Binary / categorical	Logit	Same as in primary outcome analyses, including baseline SBP
Rate of relevant side effects	Count (Poisson assumption)	Log	Same as in primary outcome analyses, including baseline SBP
Continuous laboratory measurements (potassium, sodium, urea, creatinine)	Continuous (assume normality)	Identity	Same as in primary outcome analyses

Subgroup Analyses and Heterogeneity of Intervention Effects

An exploratory objective of this study is to assess heterogeneity of treatment effect by the following potential hypothesized moderators: age, sex, and race/ethnicity. To address this, we will analyze primary and secondary blood pressure (12-week SBP, DBP) outcomes via the aforementioned

LMMs; we will add an arm-by-<potential moderator> effect in the original model specified above for each potential moderator of interest. Moderation effects will be explored via model-adjusted type III Wald test for fixed effects at the relaxed 10% level of significance. If significant, then we will examine the intervention effect within each subgroup via a series LMMs: male/female, age category, racial/ethnic category.

Agreement between Outcomes

We will use simple sample Pearson correlation coefficients (and 95% confidence limits), Bland-Altman plots, or both to examine agreement among continuous outcome measures (primarily focused on office SBP and 24-hour SBP measures). Though these analyses are not the primary focus of this trial and its results, we will use agreement analyses to make inference regarding quality of SBP measurement methods and variability.

Analyses Contingent on Add-on Therapy Requirements

If there is evidence of a difference in proportion of participants requiring amlodipine add-on therapy at six weeks across arms, then we will also explore dividing the sample into four strata: (1) those that required amlodipine add-on treatment + received active control, (2) those that required add-on + received LDQT, (3) those that did not require add-on + received active control, and (4) those that did not require add-on and received LDQT. Depending on cell counts, we will attempt a series of exploratory analyses for key outcomes (SBP, DBP) to evaluate an effect. Additional analyses of this nature will be indicated as exploratory.

